Test Group III, (regardless of risk) – First 3-months postoperation, Coumadin at an INR target of 2.5 to 3.5 with 81 mg/day (75 mg/day in Italy) aspirin will be used. After 3-months, Coumadin dose will be reduced to an INR target of 2.0 to 2.5 with 81 mg/day (75 mg/day in Italy) of aspirin continued.

Control Group – Postoperatively Coumadin with an INR target on 2.5 to 3.5 with 81 mg/day (75 mg/day in Italy) aspirin throughout the study.

D. Sample Size

A sample size estimate was conducted based on FDA OPC criteria^[1]. The study is expected to test the safety of low dose (LD) therapy for anticoagulant therapy in On-X valve patients with LD therapy consisting of the use of Coumadin in combination with aspirin or the use of antiplatelet therapy alone. This study is designed as a non-inferiority study requiring only that LD therapy is not inferior to standard

Coumadin/aspirin treatment. Testing the superiority of LD therapy with adverse event rates as low as expected would require exposure of a prohibitively large patient group. It was necessary for the sample size calculation to assume an acceptable event rate for the primary endpoints of thromboembolism, thrombosis and bleeding events derived by summing the FDA OPC's. The incident rate of the sum of these three events needs to be at least as low as the OPC sum, 7.3%. Table 1 gives the resulting sample size requirements based on a variety of outcomes.

The number of patients to be enrolled in the clinical trial is based first on the ability to show that linearized adverse event rates for the primary endpoints in the test groups are not inferior to the corresponding control groups and second on the ability to show that all valve related adverse event rates in the test groups do not equal or exceed 2 times the rates determined to be acceptable for mechanical valves.

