For the first criterion above, the test group will need to have less than 6%/ptyr cumulative rate of the three events for the study to reach significance with a randomized patient population of between 150 and 250 per group followed for between 5 and 6.7 years at a statistical power of 80% with type I error of 0.05 and a maximum allowable difference between groups of 1.5%. It is expected that each of 50 centers will be able to enroll an average of 30 patients into the study balanced to provide adequate population in each sub-group, providing sufficient patient-years to test the hypothesis, which under the above conditions is around 1000 as shown in Table 1. Thus the study has 200 patients per group in AVR high risk with an average of 5 years of follow-up, or alternatively 150 patients in AVR low risk averaging 6.7 years of follow-up and and up to 250 MVR averaging 4 years of follow-up, providing the approximately 1000 patient-years per group estimated to meet hypothesis.

For the second criterion above, the established rates are the objective performance criteria (OPC) given in the FDA guidance document ⁽¹⁾. The adverse event rates for which OPCs are established include the primary endpoints of thrombosis, thromboembolism and bleeding and the secondary endpoints of paravalvular leak and endocarditis as listed below:

% per valve year (R_A)
0.8
3.0
3.5
1.5
1.2
1.2

In the comparison to OPCs for each adverse event, the null hypothesis being tested is that the true adverse event rate for each test group is equal to or greater than twice the acceptable rate. Rejecting the null hypothesis would conclude that the rate for the test groups is less than two times the acceptable rate. The null and alternative hypotheses can be written as:

Null hypothesis:	$R \ge 2R_A$
Alternative hypothesis:	$R < 2R_A$

Table 1

Sample Size Estimation for On-X Trial LD Therapy vs. Control

The sample size estimation is based on one-sided proportion test, which tests that the incidence rate of thrombosis, thromboembolism and hemorrhage in the LD therapy groups are at least as low as the control groups.

				Maximum Allowable	
Type I Error	Statistical	Expected	Expected	Difference	Needed
(One-sided	Power	Proportion	Proportion	between Two Groups	Patient
Test)		In Control	In Low Dose	to Declare Non-inferiority	Years
		Group	Group		
0.05	80%	7.3%	4.5%	2.0%	309
			5.0%	2.0%	398
			6.0%	2.0%	719
			7.3%	2.0%	2112
			4.5%	1.5%	381
			5.0%	1.5%	504
			6.0%	1.5%	992
			7.3%	1.5%	3739

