The primary study endpoints are the rates of occurrence of valve thrombosis, thromboembolism, all major and minor bleeding events whether or not related to drug therapy, reoperation, explant and death. Other valve related adverse events including endocarditis, hemolysis, hemolytic anemia, paravalvular leak and structural and non-structural dysfunction are secondary endpoints. All events shall be as defined by the AATS/STS guidelines ^[2] for reporting valve study results.

Effectiveness -

Effectiveness endpoints are also secondary endpoints and shall be New York Heart Association (NYHA) functional classification and the echocardiographic hemodynamic parameters of peak and mean gradient and effective orifice area (EOA). Echocardiographic exams shall also evaluate indexed EOA, performance index, cardiac output, cardiac index and amount and location of any valvular regurgitation.

B. Follow-up Regime and Intervals

The intent of the study design is to treat mechanical valve patients with less aggressive anticoagulation. The control group drug regimes are those from the recommendations for mechanical valves of the ACCP^[3] and the AHA/ACC^[4], while test group regimes are either a clopidogrel/aspirin mix for low risk aortic patients or reduced Coumadin to just below the present recommendations but with aspirin added. Patients will be maintained on Coumadin/aspirin beginning immediately postoperatively, with heparin used from operation until INR target is reached. Randomization and transfer to test group will occur at the 3-month visit. INR control will be accomplished using home monitoring with the system provided by QAS or in Italy with systems as provided within the processes used in medical care there. The patient in consultation with his/her physician will also make drug dosage adjustments.

Patients will be followed at 3 months, 6 months and 1-year, then annually thereafter until the study is completed when the patient groups reach sufficient patient-years experience at up to 8-years of follow-up for any individual patient and at least 1-year follow-up for all patients. Visits will be scheduled within 1-month of the appropriate anniversary. Follow-up will be conducted by physician visit.

C. Investigational Procedures

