For any thromboembolic event it is important to determine the INR of the patient at the time of the event, if possible. Every attempt should be made to do so.

Bleeding Events

Hemorrhage is defined as any episode of internal or external bleeding in patients whether or not they are receiving anticoagulant therapy. This also includes any episode of hemorrhagic tamponade. Any anticoagulants used and INR at the time of hemorrhage should be determined, if possible. These events will be classified as major or minor, and are defined as follows.

• Major: An episode of internal or external bleeding that causes death, stroke, operation, hospitalization, or requires transfusion or pericardiocentesis. Examples include nosebleeds that require outpatient transfusion, cerebral bleeding that results in neurological damage and/or death, and gastrointestinal bleeding that requires hospitalization.

• Minor: All other episodes of internal or external loss of blood. Examples include nosebleeds that do not require transfusion, hematomas due to trauma or surgery that do not require transfusion, and ocular hemorrhage. Bleeding from open traumatic wounds (cuts, abrasions, etc.) are excluded, unless the bleeding goes uncontrolled enough to require intervention that would place the event in the major category.

Prosthetic Valve Endocarditis

Prosthetic valve endocarditis is defined as documented evidence of infection of the prosthesis based on histopathological evidence in a surgical or autopsy specimen and/or customary clinical criteria, including an appropriate combination of positive blood cultures, clinical signs (fever, new/altered cardiac murmurs, splenomegaly, systemic emboli, and immunopathological lesions). The organism(s) involved should be identified whenever possible.

Prosthetic Valve Dysfunction

Prosthetic valve dysfunction is defined as any change in valve performance which results from intrinsic or extrinsic abnormalities that cause stenosis or regurgitation. Prosthetic valve dysfunction can be classified as structural deterioration, nonstructural dysfunction, or paravalvular leak.

a. Structural Valve Deterioration

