2.3 Study Endpoints

2.3.1 Safety

The primary study endpoints are the binary measures of occurrence or not of valve thrombosis, thromboembolism (TE), all major and minor bleeding events, whether or not related to drug therapy, reoperation, explant and death. The sum of all TEs (including valve thrombosis events) and major bleeding is used as the primary decision criterion for the primary endpoints.

Secondary safety study endpoints are other valve related adverse events (AEs) including the occurrence or not of endocarditis, hemolysis, hemolytic anemia, paravalvular leak and structural and non-structural dysfunction. All events shall be as defined by the AATS/STS guidelines [Akins CW, Miller DC, Turino MI, et al] for reporting valve study results.

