4. SAMPLE SIZE CONSIDERATIONS

The study is expected to test the safety of low dose (LD) therapy for anticoagulant therapy in On-X valve patients with LD therapy consisting of the use of Coumadin® in combination with aspirin or the use of antiplatelet therapy alone. The sample size for this study was designed as a non-inferiority study requiring only that LD therapy is not inferior to standard Coumadin®/aspirin treatment. It was necessary for the sample size calculation to assume an acceptable event rate for the primary endpoints of thromboembolism, thrombosis and bleeding events derived by summing the FDA OPC's. The incident rate of the sum of these three events needs to be at least as low as the OPC sum, 7.3%.

The test group will need to have less than 6%/ptyr cumulative rate of the three events for the study to reach significance with a patient population of 200 per group followed for 5 years at a statistical power of 80% with type I error of 0.05 and a maximum allowable difference between groups of 1.5%.

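### The SAP decides on thromboembolism plus major bleeding, but the 7.3% benchmark, under-6% rate, 1.5-point margin and 80% power are stated for a sum with bleeding not limited to major

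*SAP*

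**What the plan says.** SAP 2.3.1 (Safety) lists bleeding of both grades among the primary endpoints, with valve thrombosis, thromboembolism (TE), reoperation, explant and death. It then picks one sum to decide: "The sum of all TEs (including valve thrombosis events) and major bleeding is used as the primary decision criterion for the primary endpoints".

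SAP 4 gives the planning figures for three events: TE, thrombosis and bleeding. It states that "The incident rate of the sum of these three events needs to be at least as low as the OPC sum, 7.3" per cent. It asks for a test-group rate below 6% per patient-year for the same three events, "at a statistical power of 80% with type I error of 0.05 and a maximum allowable difference between groups of 1.5" percentage points.

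Protocol II.D does the same. It assumes an "acceptable event rate for the primary endpoints of thromboembolism, thrombosis and bleeding events derived by summing the FDA" OPC rates and says that "the test group will need to have less than 6%/ptyr cumulative rate of the three events for the study to reach significance". The note to Table 1 describes a test that "the incidence rate of thrombosis, thromboembolism and hemorrhage in the LD therapy groups are at least as low as the control groups".

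None of these sample-size sentences restricts bleeding to major. Protocol III.A (Endpoints) counts "all major and minor bleeding events whether or not related to drug therapy". The Bleeding Events definition in III.C reads "Hemorrhage is defined as any episode of internal or external bleeding in patients whether or not they are receiving anticoagulant therapy", and then grades events as major or minor.

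SAP 9.1 mentions the deciding sum once, as an addition to the primary endpoint analyses, and gives it no benchmark, expected rate, margin or power. The SAP is dated 18 April 2011. Protocol Rev. N, dated March 3, 2014, still plans on the three-event sum.

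**The concern.** A non-inferiority margin has meaning only for a named endpoint with a stated control rate. Here the endpoint that decides is narrower, on the ordinary reading of the definitions, than the one for which the figures are given. A reader cannot tell which control and low-dose rates the deciding test was planned on, or how large 1.5 points is relative to its control rate.

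Two analysts could also apply the same 1.5 points to different sums, one to the three-event sum and one to TE plus major bleeding, and reach different conclusions from the same data. If the 7.3% ceiling is applied unchanged to a sum without minor bleeding, it is easier to meet than it was for the sum it was built from.

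**Working it through.** **Inputs.** Control 7.3%, low dose 6.0%, margin 1.5 points, one-sided 0.05, power 80%, and 992 patient-years (Protocol Table 1). About 1000 patient-years per group (Protocol II.D; 200 patients for 5 years in SAP 4). OPC rates 0.8, 3.0, 3.5, 1.5, 1.2 and 1.2 (Protocol II.D). The row labels of that table are not legible in the text available to me.

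**Which OPC values make up 7.3.** Of all 63 non-empty subsets of the six values, only 0.8 + 3.0 + 3.5 gives 7.3. This identifies the numbers that were added, not how the 3.5 row is labelled.

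**The plan's own figure.** I used the Farrington-Manning score test with equal arms:

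- n per arm = (1.645·s0 + 0.842·s1)² / (m + pc − pt)²
- power = Φ{[(m + pc − pt)·√n − 1.645·s0] / s1}

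Here s1 = √[pt(1−pt) + pc(1−pc)], and s0 is the same expression at the maximum-likelihood rates restricted to pt − pc = m.

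For pc = 7.3%, pt = 6.0%, m = 1.5 points, the restricted rates are 7.54% and 6.04%, so s0 = 0.3557 and s1 = 0.3522. The denominator is (0.015 + 0.013)² = 0.000784, and n = 991.2, rounded up to 992. This matches Table 1, and the same method reproduces all 24 rows. At n = 1000: (0.028 × 31.623 − 1.645 × 0.3557) / 0.3522 = 0.853, and Φ(0.853) = 80%.

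**The under-6% condition belongs to 7.3%.** At 1000 patient-years per arm and m = 1.5 points, the highest low-dose rate that still gives 80% power is 6.01% against a 7.3% control. With a lower control rate the limit falls (below).

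**Illustration for the deciding sum.** Assumption: the unused value 1.5 is a major-bleeding rate, so the matching sum is 0.8 + 3.0 + 1.5 = 5.3%. The documents as I can read them do not confirm this. Power at 1000 patient-years per arm:

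| Low-dose rate | Margin | Control 7.3% | Control 5.3% |
|---|---|---|---|
| Planned ratio 6.0/7.3 (6.0%; 4.36%) | 1.5 points | 80% | 81% |
| Planned 1.3-point gap (6.0%; 4.0%) | 1.5 points | 80% | 90% |
| Equal rates | 1.5 points | 36% | 44% |
| Planned ratio | 20.5% of control (1.5; 1.09 points) | 80% | 68% |

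First row at 5.3%: s0 = 0.3081, s1 = 0.3031, (0.02444 × 31.623 − 1.645 × 0.3081) / 0.3031 = 0.878, Φ = 81%. Last row: the margin is 1.5 × 5.3/7.3 = 1.09 points, s0 = 0.3062, (0.02033 × 31.623 − 1.645 × 0.3062) / 0.3031 = 0.459, Φ = 68%.

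**Relative margin.** 1.5/7.3 = 20.5%; 1.5/5.3 = 28.3%.

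**Range without that label.** If the rows follow the order in which the text names the events (also an assumption), the matching sum lies between 0.8 + 3.0 = 3.8% (no major bleeding at all) and 7.3%. The limit for 80% power is then between 3.22% and 6.01% (4.39% at a 5.3% control), and the margin is between 39.5% and 20.5% of control. Power at the planned ratio with a 1.5-point margin is 83% at a 3.8% control.

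**The case against.** The strongest reply is that the sample-size text never says minor bleeding is included. If bleeding there means major bleeding, and the 3.5 row is a major-bleeding rate, then 7.3% is already the sum of the deciding events and only a word is missing. The illegible row labels prevent me from excluding this. The definitions in Protocol III.A and III.C and the list in SAP 2.3.1 make it the less natural reading, because each counts minor bleeding. The point survives either way, since the SAP would still have to say that the planned sum and the deciding sum are the same.

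A second reply is that the benchmark may not be missing at all. Protocol II.D names five event types but lists six rates, so the labelled table may hold a separate major-bleeding rate. That is possible. It would supply a benchmark, but not an assumed low-dose rate, margin or power for the deciding sum.

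Third, a reader might infer that narrowing the endpoint leaves the trial underpowered. The documents do not support that. Compared like for like with the stated absolute margin, power at the illustrative 5.3% control is the same or higher than at 7.3%. It drops only if the margin is treated as a fixed share of the control rate, and no section states a relative margin. Nor should the 6% planning rate be set against a 5.3% benchmark, because 6% was stated for the three events.

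**Conclusion.** The point holds as a mismatch between the sum that is planned on and the sum that decides; it should be fixed. The benchmark of 7.3%, the rate below 6%, the 1.5-point margin and the 80% power should not be quoted for TE plus major bleeding until they are restated for it.

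The effect is on meaning and stringency. The 7.3% ceiling becomes more lenient for a narrower sum, and the fixed margin grows from 20.5% of control to an illustrative 28%. The arithmetic behind Table 1 is correct for the sum it describes.

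This rests on two readings: that bleeding in the sample-size text includes minor bleeding, which is inferred from the definitions, and, for the 5.3% figures only, that the unlabelled 1.5 is major bleeding. Two further conclusions would go too far: that the trial lacks power, and that choosing major bleeding was an error. The documents show neither.

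**What to change.** Keep TE, including valve thrombosis, plus major bleeding as the decision criterion. Then:

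- In SAP 4 and Protocol II.D, restate for that sum the OPC benchmark, the assumed low-dose rate, the margin with its justification, and the resulting power.
- Take the benchmark from the labelled OPC table and name its source. The protocol cites the 1994 draft guidance, while the SAP cites ISO 5840:2005 and the 2010 draft guidance.
- In SAP 9.1, name this composite and its margin as the deciding comparison, and report the all-bleeding sum as supportive.
- Make these changes without sight of results by arm.

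The reverse course, moving the decision to the all-bleeding sum, would leave the planning figures intact. But it would change the decision criterion of a running trial and bring minor bleeding into it, so it is not just an edit of wording.

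The cost is text only. CRF 4 already records bleeding as major or minor, so no new data are needed. The downside is that the restated power, or the margin as a share of control, may look less favourable than the present figures.

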2.3.2 Efficacy

Effectiveness endpoints are also secondary endpoints and are the New York Heart Association (NYHA) functional classification scores and the echocardiographic hemodynamic measures of peak and mean gradient and effective orifice area (EOA). Echocardiographic exams are also used to evaluate indexed EOA, performance index, cardiac output, cardiac index and the amount and location of any valvular regurgitation.

3. STUDY DESIGN

3.1 Overall Study Design and Treatment Groups

This is a longitudinal, randomized (randomization to occur at the 3 month follow-up) study comparing the On-X valve on low dose anticoagulation (test group) to concomitant control groups of On-X valves receiving standard Coumadin®/aspirin therapy, and also to FDA objective performance criteria (OPC) [ISO 5840:2005 Cardiovascular implants – Cardiac valve prostheses and Draft guidance for industry and FDA staff – Heart valves – Investigational Device Exemption (IDE) and Premarket Approval (PMA) applications, January 20, 2010]. It is a multicenter study consisting of 40 centers in the United States enrolling no more than 1200 patients (200 in each of 6 groups)

18 April 2011

[figure not shown]
Overall Schedule of Time and Events 3.2

5+ Year 5 Year 4 Year 3 Year 2 Year 1 Year 6 Month 3 Month Discharge Operation Preoperation

Form/Data

CRF 1

Card

Death

Required only if needed Required data Not applicable

4. SAMPLE SIZE CONSIDERATIONS

The study is expected to test the safety of low dose (LD) therapy for anticoagulant therapy in On-X valve patients with LD therapy consisting of the use of Coumadin® in combination with aspirin or the use of antiplatelet therapy alone. The sample size for this study was designed as a non-inferiority study requiring only that LD therapy is not inferior to standard Coumadin®/aspirin treatment. It was necessary for the sample size calculation to assume an acceptable event rate for the primary endpoints of thromboembolism, thrombosis and bleeding events derived by summing the FDA OPC's. The incident rate of the sum of these three events needs to be at least as low as the OPC sum, 7.3%.

The test group will need to have less than 6%/ptyr cumulative rate of the three events for the study to reach significance with a patient population of 200 per group followed for 5 years at a statistical power of 80% with type I error of 0.05 and a maximum allowable difference between groups of 1.5%.

5. ANALYSIS POPULATIONS

5.1 Safety Population

The safety population will be the primary population for all analyses and includes all patients who have received at least one dose of study drug.

6. CONSIDERATIONS FOR DATA ANALYSIS

6.1 Programming Environment

All analyses will be conducted using SAS® version 9.2.

6.2 Strata and Covariates

All primary and secondary analyses utilizing Kaplan-Meier life tables will be stratified by risk factors including age and gender. Additionally, MVR treatment groups will be stratified by continent (e.g. North America vs. Italy) for all primary and secondary endpoints.

6.3 Subgroups

There are no planned subgroup analyses.

6.4 Multiple Comparisons and Multiplicity

There are no planned adjustments for multiplicity.

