6.5 Significance Level

Unless otherwise noted, all statistical analyses will be conducted with a significance level (α) of 0.05 and utilize two-sided testing.

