9. SAFETY ANALYSIS

9.1 Primary Analysis

The primary study endpoints are the binary measure of occurrence or not of valve thrombosis, thromboembolism, all major and minor bleeding events whether or not related to valve, reoperation, explant and death. Additionally, the sum of all TEs (including valve thrombosis events) and major bleeding will be included with the primary endpoint analyses.

For each of these binary endpoints, a Kaplan-Meier (KM) life table will be fitted and used to compare each valve treatment group and its control group. The KM analysis will adjust for select risk factors

including age and gender. In addition, the linearized rates as well as overall percentages of occurrences will be included in summary tables. Comparisons of overall percentages between each valve treatment group and its control will be made using a chi-square test or Fisher's exact test as appropriate. Linearized rates will be analyzed for differences between treatment and control groups with relative risks and 95% confidence intervals.

Analyses of mitral valve subjects will also be stratified by location (North America versus Italy) in the summary tables.

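### SAP 9.1 tests six 'primary' endpoints beside the decision criterion with no order or adjustment, so a regimen with no effect has roughly a 10-14% chance of a nominal benefit on one of them

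*SAP*

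**What the plan says.** SAP 2.3.1 defines the primary endpoints as "occurrence or not of valve thrombosis, thromboembolism (TE), all major and minor bleeding events, whether or not related to drug therapy, reoperation, explant and death". Counting all bleeding once, that is six. The same section then singles out one quantity: "The sum of all TEs (including valve thrombosis events) and major bleeding is used as the primary decision criterion for the primary endpoints".

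SAP 9.1 repeats the six and says that the sum "will be included with the primary endpoint analyses". For each endpoint it plans a Kaplan-Meier comparison with control, a chi-square or Fisher's exact test on overall percentages, and a relative risk with 95% confidence interval on linearized rates. All of these look for a difference. The section gives no order, no non-inferiority test and no margin. The 1.5% margin stands in SAP section 4, with the sample size.

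SAP 6.5 states that, unless otherwise noted, "all statistical analyses will be conducted with a significance level (α) of 0.05 and utilize two-sided testing". SAP 6.4 states: "There are no planned adjustments for multiplicity".

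The design is non-inferiority. On superiority, Protocol II.D (Sample Size) says: "Testing the superiority of LD therapy with adverse event rates as low as expected would require exposure of a prohibitively large patient group".

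**The concern.** The two SAP sections give the sum different standing. Section 2.3.1 makes it the basis of the decision. Section 9.1, which governs what is computed and tabulated, lists it as one more item beside six endpoints that keep the label 'primary'. Nothing in 9.1 says that the six are supportive.

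The natural product of such a plan is a table of 'primary' endpoints with a p-value against each. A low-dose advantage with p below 0.05 on one of them could then be presented as a primary result, whatever happened on the sum. All bleeding is the obvious candidate, since Protocol IV gives bleeding as the reason to reduce anticoagulation. At stake is the error rate behind such a claim, not the error rate of the non-inferiority decision.

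**Working it through.** **The plan's own figure.** The documents state no familywise error rate. The figure they rely on is 992 patient-years per group (Protocol Table 1: one-sided 0.05, 80% power, 7.3% against 6.0%, margin 1.5%). The distance to the margin is 1.5% + 1.3% = 2.8%, so

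n = (1.645 + 0.842)² × (0.073 × 0.927 + 0.060 × 0.940) / 0.028² ≈ 979,

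which is within 1.3% of 992. The trial is therefore sized for one non-inferiority test on one summed rate in each comparison. The six endpoints play no part in it.

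**Inputs for the error rate**
- Six endpoints (SAP 2.3.1 and 9.1).
- Two-sided 0.05 (SAP 6.5), so 0.025 per test in the direction of benefit.
- 200 patients per group for 5 years (SAP section 4): 200 × 5 = 1,000 patient-years.
- Event rates of 0.8, 3.0 and 3.5%/yr for thrombosis, thromboembolism and bleeding, from the OPC (objective performance criteria) list in Protocol II.D. The row labels are lost in the text available here. The assignment follows the order in which the events are named, and 0.8 + 3.0 + 3.5 = 7.3, the stated sum.
- Overlap: Protocol III.C makes thrombosis a subcategory of thromboembolism, and replacing the valve at reoperation counts as both reoperation and explant.
- Reoperation, explant and death rates are not in the documents and are assumed below.

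**Ceiling: six independent tests.** 1 − 0.975⁶ = 14.1% for at least one false benefit, and 1 − 0.95⁶ = 26.5% in either direction.

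**With overlap: simulation under identical true rates in both arms.** Rates are in %/yr. The first five rows use 200 per arm, 5 years, chi-square or Fisher by expected count, and 6,000 runs. 'Other' means events not arising from those already listed.

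| Scenario | At least one false benefit |
|---|---|
| OPC rates; other reoperation 0.8, other death 2.0 | 11.8% |
| Other reoperation 0.3, other death 1.0 | 11.0% |
| Other reoperation 1.5, other death 3.0 | 11.2% |
| Thrombosis not nested in thromboembolism; other reoperation 1.0, other death 2.0 | 12.4% |
| Thrombosis rare (0.2, other thromboembolism 2.0); other reoperation 0.5, other death 1.5 | 9.6% |
| Poisson counts, z = (x − y)/√(x + y), 200,000 runs; reoperation 1.0, explant 0.5, death 2.0 | 12.8% |

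Simulation error for the 6,000-run rows is about √(0.12 × 0.88 / 6,000) = 0.4 percentage points. The results fall below 14.1% because endpoints overlap and because rare endpoints seldom reach significance: in the rare-thrombosis row, thrombosis alone gives a false benefit in 0.3% of trials. An exact conditional rate test, which SAP 9.1 does not name, gives a lower figure still, 8.5%.

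**Size.** 9.6 / 2.5 = 3.8 and 14.1 / 2.5 = 5.6, so the chance of a spurious nominal benefit is about four to six times the nominal one.

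**The decision criterion.** The sum is one test per regimen. A difference test on it gives a false benefit in 2.5% of trials, and a non-inferiority test runs at its own stated level. Neither depends on what the six show.

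**The case against.** The strongest reply is that SAP 2.3.1 already names one decision criterion and SAP 9.1 does not revoke it. The six are not six routes to success, and neither document says that a significant advantage on one component counts as a success. This stands. A reader might infer that the trial's conclusion carries a 13% error rate; the documents do not support that.

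A reader might also multiply up to the three regimens, 1 − (1 − 0.13)³ = 34%. That figure should not be used as a headline. Each regimen has its own patients, its own control group and its own question (SAP 2.2), so control across regimens is debatable, and the fix below does not attempt it.

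The six are also safety endpoints, and leaving safety comparisons unadjusted is an accepted choice that avoids masking harm. SAP 6.4 is thus a deliberate statement, not an omission. This is sound for findings of harm. It does not justify claims of benefit from the same unadjusted tests.

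Finally, three of the six rates are assumed. That is why a range is given. Moving other reoperation from 0.3 to 1.5%/yr and other death from 1 to 3%/yr changes the chi-square/Fisher result by less than one percentage point. Making thrombosis rare matters more.

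What the reply does not answer is the drafting. SAP 9.1 keeps the label 'primary' on all six, tests each for a difference, and gives the sum neither precedence nor a non-inferiority test.

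**Conclusion.** The point holds in limited form. SAP 2.3.1 and 9.1 need to be reconciled, and SAP 6.4 leaves claims of benefit on the six 'primary' endpoints without error control. Within one test-versus-control comparison, a regimen with no real effect has roughly a 10-14% chance of a nominally significant benefit on at least one of them. This assumes identical true rates in both arms, 200 patients per arm followed for 5 years, the OPC rates (or lower ones for thrombosis and thromboembolism), and the assumed reoperation, explant and death rates. An exact rate test would go slightly below the range.

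The non-inferiority decision on the sum is not inflated. The issue is how component results may be labelled and claimed. It is worth correcting because the correction is cheap.

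**What to change.** Amend SAP 6.4 and 9.1 as follows, separately for each test-versus-control comparison:

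1. The non-inferiority test of all TEs plus major bleeding is the only confirmatory test. Write it into 9.1 with the 1.5% margin from SAP section 4 and an explicit one-sided level. At present Protocol Table 1 is one-sided, while SAP 6.5 says two-sided unless noted.
2. The six listed endpoints are supportive. Report rates and 95% confidence intervals, and make no claim of benefit from them.
3. Findings of harm on any endpoint are reported unadjusted.
4. Optional, if the sponsor wants a claim of fewer bleeds: test all bleeding next in fixed sequence at the same level, only if non-inferiority is met. The protocol itself says that the trial is not sized for superiority.

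Keeping all six confirmatory with a Bonferroni level of 0.05/6 = 0.0083 two-sided would also hold false benefit to at most 2.5% per regimen, but at a stricter threshold for every endpoint.

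Cost: SAP text, including a non-inferiority test that 9.1 does not yet contain. The decision criterion loses no power. The sponsor gives up nominal benefit claims on thrombosis, thromboembolism, reoperation, explant and death, and on bleeding too unless step 4 is adopted and its condition met.
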